7.2.1 Adverse Events and Serious Adverse Events

Adverse events whether reported, observed, or elicited by indirect questioning will be captured from the time of infusion start through 10 days post-infusion (Days 1-15). SAEs will be captured from the time of infusion start throughout the course of the subject's participation in the study (6 months). The AE/SAE relationship to the study treatment will be judged as not related, possibly related, probably related, or related. Ongoing AEs will be followed to resolution, whenever possible.

Particular attention should be paid to the following potential risks previously identified as associated with administration of progesterone: serious thromboembolic events such as thrombotic myocardial infarction, pulmonary embolism, deep vein thrombosis, ischemic stroke; allergic reactions; marked liver function abnormalities; serious infections such as pneumonia, sepsis, meningitis.

All SAEs will be reported by telephone or written report within 24 hours of being notified of the event to the Sponsor's Medical Monitor and then reported to each site's IRB/IEC according to the local regulations. Serious adverse events that persist at Month 6 post-injury will be documented as to their final status.

7.2.2 ECG

The ECGs will be analyzed at the site and documented on the CRF by the Investigator. All clinically significant abnormal ECGs, assessed for clinical relevance by the Investigator, must be documented as an AE on the CRF.

7.2.3 Laboratory Safety Tests

Standard clinical safety labs will be measured locally at the sites and recorded for the specified time points (see [Appendix B](#) for details). The Investigator will assess all abnormal lab values at these time points for clinical significance; if categorized as adverse events, they will be collected and recorded similarly to other AEs. All clinically significant abnormal lab values will be followed until resolution, whether or not they are deemed AEs by the investigator. If resolution is not seen, a justification as to the cause for such an abnormality, such as if due to an underlying pre-existing condition, associated co-morbidity, etc, will be recorded.

7.2.4 Vital Signs

Vital signs (heart rate (bpm), respiration rate (per min), systolic and diastolic blood pressure (mm Hg), and temperature (C°), and pupil response) will be monitored in parallel with and per the same timing as ICP and TIL (Sections [7.3.4](#) and [7.3.5](#) below).

7.2.5 Daily Fluid Balance

The total amount of fluids administered and the total excreted once per 24 hour period will be recorded during Day 1 through Day 6.

7.2.6 Arterial Blood Gases

While the subject is intubated, the highest value of the day for the PaCO₂ and the lowest value of the day for PaO₂, pH, HCO₃ and SaO₂ along with the accompanying Fio₂ setting will be recorded before randomization (Day 1 pre-dose) and daily during Day 1 through Day 6.

7.2.7 Neuroworsening

Instances of neuroworsening will be recorded daily from Day 1 through Day 15. Neuroworsening is defined as any one of the following: a decrease in GCS motor score ≥ 2 , development of pupillary abnormalities, any other neurological deterioration or progression of lesion on CT scan leading to a change in patient management.

7.3 Selection of Efficacy Measurements Related To Management of TBI

7.3.1 Glasgow Outcome Scale (GOS)

The GOS (Jennett and Bond, 1975) is the primary endpoint of this study and assesses mortality and disability in TBI patients according to the designation Good Recovery, Moderate Disability, Severe Disability, Vegetative State or Dead. The GOS will be administered using a standard questionnaire and accompanying narratives at 3 and 6 months post-injury. A baseline narrative will also be recorded by the Investigator. A central review will be performed of all GOS recordings.

7.3.2 Glasgow Outcome Scale - Extended (GOS-E)

The GOS-E will be administered at 3 months and 6 months post injury. A standardized questionnaire structuring the interview will be used, as well as the narrative completed by the Investigator. A central review will be performed of all GOS-E recordings.

The GOS-E assessment of mortality and disability in TBI patients extends the original five GOS categories of functional outcome to eight categories (Jennett *et al.*, 1981; Wilson *et al.*, 1998; Teasdale *et al.*, 1998):

- Dead
- Vegetative State
- Lower Severe Disability
- Upper Severe Disability
- Lower Moderate Disability
- Upper Moderate Disability
- Lower Good Recovery
- Upper Good Recovery

7.3.3 Mortality

Any SAE which results in death at any time during the study will be recorded both as an SAE and a Death Report. The Death Report will include the primary cause of death, secondary cause if any, and the date and time of death. If an autopsy is performed, the report should be collected and provided in a de-identified manner.

7.3.4 Intracranial Pressure/Cerebral Perfusion Pressure

If an ICP monitor is placed, ICP measures will be recorded as early as before randomization (Day 1 pre-dose, or as soon as the monitor is placed) and for up to 6 days while ICP is being monitored. The ICP will be recorded daily at the specific times of: 00:00, 06:00, 12:00 and 18:00 hour (+/- 30 minutes), along with vital signs [heart rate (bpm), respiration rate (per min), systolic and diastolic blood pressure (mmHg), temperature (C°) and pupil response]. In addition to the 4 daily timepoints, ICP and vital signs will be recorded whenever ICP management changes. If the ICP monitor is not placed, vital signs will still be collected at these four timepoints per day.

ICP will be monitored preferentially using a catheter connected to an external strain gauge (intraparenchymal ICP device or ventricular catheter for the ICP measurement). If placement of an intraventricular catheter is not possible, an intraparenchymal catheter placed away from the lesion may be used. The timing and duration of ICP monitoring will be at the discretion of the Investigator.

The CPP will be calculated automatically as the difference of mean arterial pressure and ICP, based on the blood pressure and ICP readings recorded in the eCRF.

7.3.5 Therapeutic Intensity Level (TIL)

TIL data will be recorded for up to 6 days or while ICP is being monitored. TIL scores will be automatically calculated based on the medications and procedures used to manage the subject's ICP, as recorded into the eCRF. Table 1 lists the specific known treatments commonly used to manage ICP and CPP and the corresponding scoring system (modified from Maset *et al.*, 1987). If no therapies were utilized, then the scoring is zero during a given time period.

Table 1
Therapeutic Intensity Level Grading System

| Therapy | Score |
|---------|-------|
|---------|-------|

| | |
|--|-----------|
| Surgical Decompression | 1 |
| Barbiturate Induced Coma | 1 |
| Hypothermia for ICP reduction | 1 |
| Hyperventilation (pCO ₂ <30) | 1 |
| Pressor Administration (to keep CPP 60) | 1 |
| Hypertonic Saline | 1 |
| Mannitol | 1 |
| Ventricular Drainage | 1 |
| Paralysis Induction | 1 |
| Sedation | 1 |
| Maximum Total Score | 10 |
| TIL scores will be analyzed based on the therapies recorded. Because of the stepwise progression of therapy (from sedation to barbiturate use), barbiturate administration or surgical decompression constitutes a total score of 10 when performed. | |
| Modified from Maset et al., 1987 | |

7.3.6 CT Scans

A baseline CT scan will be performed before randomization as part of eligibility assessment. A follow-up CT scan will be performed end-infusion on Day 6 (+/- 1 day) post-injury to assess the progression of lesion volume and brain edema. The findings will be classified in accordance with the Marshall criteria ([Marshall et al., 1992](#)). Baseline and Day 6 (+/- 1 Day) CT scans will be sent to the central reader, who will evaluate them for study analysis purposes only.

7.3.7 QOL SF-36

The Quality of Life (QOL) SF-36 questionnaire will be assessed at 3 and 6 months post injury. The SF-36 is a validated generic, easily administered survey of patient health consisting of eight scaled scores, which are the sums of the responses to questions in each section ([Ware and Sherbourne, 1992](#); [McHorney et al., 1993](#)). Each scale is directly transformed into a 1-100 scale on the assumption that each question carries equal weight. The eight sections are:

- Vitality
- physical functioning
- bodily pain
- general health perceptions
- role physical
- role emotional
- role mental
- mental health

The 8 scales can also be summarized into two summary scores for physical and mental health, respectively. The SF-36 must be completed by the subject.

7.3.8 Glasgow Coma Scale

The Glasgow Coma Scale ([Teasdale and Jennett, 1974](#)) will be performed before randomization and once daily (best) during Days 1 to 6 and on Day 15. The GCS is a neurological scale which aims to give a reliable, objective way of recording the conscious state of a person. A patient is assessed against each of three criteria, eye, verbal and motor responses, and the resulting values are summed for the total GCS score. The lowest possible total GCS is 3 (deep coma or death), while the highest is 15 (fully awake person).

8. STATISTICAL PLAN

8.1 Sample Size Justification

It is planned to recruit a total of 1180 patients randomized in a 1:1 ratio to BHR-100 or placebo (590 in each treatment group). This sample size estimation is based on the use of a proportional odds model ([Whitehead, 1993](#)) to analyze the primary outcome variable, namely the conventional 5-point GOS at six months after injury. Assuming approximately 31% good outcome, 21% moderate disability, 19% severe disability and 29% combined vegetative state and death, the total sample size of 1180 subjects will give 90% power to detect a common odds ratio of 1.5 of improvement in outcome (i.e. 10% effect size) at the 1% significance level (two-sided). The baseline outcome distribution used is based on the six-month GOS outcome distribution from the head injury population with GCS 3-8 in the previous TBI Phase 3 trials in the International Mission for Prognosis and Analysis of Clinical Trials in TBI Project (IMPACT) Database ([Marmarou et al., 2007](#)).

8.2 Baseline Data

Baseline comparability of the randomized groups will be illustrated using appropriate descriptive statistics.

8.3 Primary Efficacy Analysis

The primary efficacy variable is GOS evaluated at 6 months post injury.

The proportional odds model (POM) ([McCullagh, 1980](#)) will be used to compare BHR-100 to placebo for the GOS outcome at six months (categories of good recovery, moderate disability, severe disability, and the combined vegetative state/death). A test for the proportional odds assumption will be conducted and if statistically significant, other polytomous logistic models will be investigated. The analyses will be conducted on an intent-to-treat (ITT, i.e. all randomized subjects) basis, and the POM will be fitted including the effect of treatment, geographic region (North America, Europe, Asia, and South America), age, GCS motor score, pupil response, and CT classification.

If the p-value from the test of the null hypothesis is less than 0.0003 (at the interim analysis) or 0.0098 (at the final analysis), it will be concluded that BHR-100 is statistically significantly different from placebo with respect to the GOS at 6 months following injury.

In the event that the primary efficacy analysis does not show statistical significance at the study wise 1% significance level, i.e. the final analysis p-value is not less than 0.0098, a final adjusted p-value will be calculated and the result considered statistically significant at the 5% level if the adjusted p-value is less than 0.05. The adjusted p-value will be calculated using EAST® (Cytel Statistical Software, Cambridge, MA) or other appropriate statistical software package to adjust for the interim analysis using the pre-specified boundaries.

8.3.1 Alternate Primary Efficacy Analysis: Sliding Dichotomy Model

If the proportional odds assumption cannot be justified, an analysis will be conducted using a sliding dichotomy ([Maas et al., 2006](#); [Murray et al., 2005](#)) of the GOS outcome at 6 months following injury, following categorization of patients into different prognosis groups (worst,

intermediate, and best) based on baseline prognostic factors. The hypothesis that the proportion of favorable responses observed in each treatment group is the same will be tested both within the baseline prognosis grouping (best, intermediate and worst) and overall using the Cochran-Mantel Haenszel Chi-Square test, adjusted for region.

If the p-value from the test of the null hypothesis of no difference in the proportion of favorable responses observed in each treatment group is less than 0.0003 (at the interim) or 0.0098 (at the final analysis), it will be concluded that there is a statistically significantly difference in the proportion of favorable responses between the 2 treatment groups.

If this analysis is not required as an alternate analysis to the Proportional Odds Model analysis, it will still be performed as an additional sensitivity analysis.

8.3.2 Sensitivity Analysis: Dichotomized Model

In addition, the GOS at 6 months post injury will be dichotomized into Good Recovery, Moderate Disability versus Severe Disability, Vegetative Status/Dead.

The binary outcome will be analyzed using logistic regression analysis. The logistic regression model will be fitted including the effect of treatment, geographic region (North America, Europe, Asia, and South America), age, GCS motor score, pupil response, and CT classification.

The logistic regression model will be used to test the null hypothesis that the odds of an ‘event’, i.e. observing a response of moderate disability or good recovery on the outcome variable, GOS at 6 months following injury, adjusted for region, age, GCS motor score, pupil response, and CT classification is the same in both treatment groups, i.e.

Null Hypothesis: $H_0 : \beta_1 = 0$

Alternative Hypothesis: $H_1 : \beta_1 \neq 0$

If the p-value from the test of the null hypothesis of $\beta_1 = 0$ is less than 0.05, it will be concluded that BHR-100 is statistically significantly different from placebo with respect to the GOS at 6 months following injury. The odds of an ‘event’ (moderate disability, or good recovery) in the GOS at 6 months will be modeled and the corresponding common odds ratio for treatment, e^{β_1} , can then be interpreted to determine the direction of the treatment difference as follows: with the placebo group being considered as the reference category, if the odds ratio (OR_{BHR-100/placebo}) is greater than 1, the odds of a favorable outcome in the GOS at 6 months is greater in the BHR-100 treatment group compared to placebo.

8.3.3 Handling of Missing Primary Efficacy Endpoint Data

When the primary efficacy endpoint is missing, the last observation carried forward (LOCF) principle will be used to populate the primary endpoint, i.e. the Month 3 GOS assessment will be carried forward. In the event that a subject has neither the 3 nor the 6-month GOS, the missing values would be imputed based upon the proportional odds model. It is anticipated that there will be minimal missing data, however sensitivity analyses will be carried out, if necessary, to confirm that the imputation method(s) did not have an impact on the primary efficacy analysis results.

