When the primary efficacy endpoint is missing, the last observation carried forward (LOCF) principle will be used to populate the primary endpoint, i.e. the Month 3 GOS assessment will be carried forward. In the event that a subject is lost to follow-up and has neither the 3 nor the 6-month GOS, the missing values will be imputed based upon the primary proportional odds model (POM).

To obtain values for the missing responses using the POM the predicted response probabilities will be used. Specifying the PREDICTED option on the OUTPUT statement of PROC LOGISTIC, 3 (number of categories in response variable – 1) predicted probabilities will be provided for each subject; these are the ordered cumulative probability of each response category, i.e.

$$\text{Probability}(Y \leq 1) = P(Y=1) = \text{Probability GOS}=1$$

$$P(Y \leq 2) = \text{Probability that GOS is 1 or 2}$$

$$P(Y \leq 3) = \text{Probability that GOS is 1, 2 or 3}$$

Therefore, to obtain the predicted probability of each individual response, for example, the probability that the response was GOS=2, the following calculation is performed:

$$P(Y=2) = P(Y \leq 2) - P(Y \leq 1)$$

Similarly,

$$P(Y=3) = P(Y \leq 3) - P(Y \leq 2)$$

and finally,

$$P(Y=4) = 1 - [P(Y \leq 3)]$$

since the individual probabilities must sum to one.

The missing GOS response will then be set to the most probable category, i.e. the response with the largest predicted probability.

It is anticipated that there will be minimal missing data, however sensitivity analyses will be carried out to confirm that the imputation method(s) did not have an impact on the primary efficacy analysis results. Therefore, the primary efficacy analyses will also be conducted on observed values only, without any imputation.

Covariates, missing data imputation

For the primary efficacy analyses, missing data for the following covariates will be imputed as the most commonly occurring value over subjects with non-missing data: motor response component of GCS, pupillary response, presence of hypoxia, presence of hypotension, CT classification, and presence of traumatic subarachnoid hemorrhage.

GOS assessment – Dead responses

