Subjects without a GOS response assessment at Month 6 but who have a death date from the Death Report eCRF within 6 months + 28 days of their randomization date (calculated as death date – randomization date + 1 \leq 208) will be assigned a Month 6 GOS response of Dead. Similarly, subjects without a GOS response assessment at Month 3 but who have a death date from the Death Report eCRF within 3 months + 28 days of their randomization date (calculated as death date – randomization date + 1 \leq 118) will be assigned a Month 3 GOS response of Dead.

Secondary Endpoint: Mortality at Month 1

Survival status from the date of injury (Day 1 of the study) until Day 30 (Month 1) will be monitored and recorded as lost to follow-up, consent withdrawn, alive, dead or other. Only subjects with a mortality assessment post-injury of alive or dead will be used in the assessment of mortality.

Secondary Endpoint: Mortality at Month 6

Survival status from the date of injury (Day 1 of the study) until Day 180 (Month 6) will be monitored and recorded as lost to follow-up, consent withdrawn, alive, dead or other. Only subjects with a mortality assessment post-injury of alive or dead will be used in the assessment of mortality.

Time to death

The time to death (in days) will be defined as:

$$\text{Date of death} - \text{date of TBI} + 1$$

If a subject does not die during the conduct of the study, they will be censored at the earliest (minimum) of their Month 6 GOS assessment date and end of study date, and censor time (in days) will be defined as:

$$\text{Minimum(month 6 GOS assessment date, end of study date)} - \text{date of TBI} + 1$$

Since subjects were not followed for death after their Month 6 GOS assessment, subjects who have a death recorded after the assessment will be censored on the date of their Month 6 assessment.

Exploratory Endpoint: CPP

The following formulae are used to derive CPP:

$$\text{Mean Arterial Pressure (MAP)} = \frac{2}{3} \text{ diastolic BP} + \frac{1}{3} \text{ systolic BP};$$

$$\text{CPP} = \text{MAP} - \text{ICP}.$$

MAP will be recorded as missing if either systolic BP and/or diastolic BP measurements are not recorded. CPP will be calculated where MAP and ICP have both been recorded; if either is missing the CPP will be recorded as missing.

Exploratory Endpoint: TIL

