9.5 Efficacy Analyses

9.5.1 Primary Efficacy Analysis

The primary efficacy variable is GOS evaluated at 6 months post injury. The primary analysis will be based on imputation of missing data as described in Section 5.

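### A missing 6-month GOS is filled with one value (Month 3 carried forward, or a modal category), which can bias the primary odds ratio in either direction and leaves imputation uncertainty out of the interval

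*Protocol*

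**What the plan says.** Protocol 8.3.3 fills a missing 6-month GOS from the earlier visit: "the Month 3 GOS assessment will be carried forward". SAP Section 5 says the same: "When the primary efficacy endpoint is missing, the last observation carried forward (LOCF) principle will be used to populate the primary endpoint". Subjects with neither assessment get predicted probabilities from the primary proportional odds model (POM), reduced to one value: "The missing GOS response will then be set to the most probable category". SAP 9.5.1 places all this in the primary analysis: "The primary analysis will be based on imputation of missing data as described in Section 5".

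Known deaths are handled separately. A subject with no Month 6 GOS but a recorded death within 208 days of randomization "will be assigned a Month 6 GOS response of Dead", so an earlier score does not overwrite a death. Carry-forward therefore reaches only subjects who have a Month 3 GOS, have no Month 6 GOS and are not known to have died.

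The check on the imputation is conditional in Protocol 8.3.3: "sensitivity analyses will be carried out, if necessary, to confirm that the imputation method(s) did not have an impact". The SAP makes it firm: "the primary efficacy analyses will also be conducted on observed values only, without any imputation". SAP 9.5.1.1 to 9.5.1.3 repeat the observed-case analysis for the POM, the sliding dichotomy and the dichotomized model, in the modified intention-to-treat and per-protocol populations. Neither document plans multiple imputation or a tipping-point analysis. Both expect little missing data, and neither gives a missingness rate or any Month 3 to Month 6 transition rates.

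**The concern.** Three features of the rule are weak.

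- **No change is assumed after Month 3.** Subjects known to be dead are excluded from carry-forward, so it acts mainly on survivors, who are the ones able to improve. If one arm loses more survivors, or its missing survivors recover more, that arm's Month 6 distribution is pulled down further. Deterioration between visits is ignored too.
- **A filled value counts as an observation.** Uncertainty about the true Month 6 category does not enter the standard error.
- **The modal-category fallback has the same fault.** At the planning proportions the two largest categories are good recovery (31%) and vegetative state or death (29%). Moderate (21%) and severe disability (19%) would probably be chosen less often than they occur. A subject not known to be dead can be placed in the worst category.

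At stake are the size of the primary odds ratio, some power, and whether the planned check would reveal a problem.

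**Working it through.** **Reproducing the plan's sample size.** Inputs from Protocol 8.1: placebo 31% good recovery, 21% moderate, 19% severe, 29% vegetative or dead; OR 1.5; two-sided 1%; 90% power; 1:1. Applying OR 1.5 at each cut gives BHR-100 0.4026, 0.2165, 0.1669, 0.2140. Mean proportions are 0.3563, 0.2132, 0.1785, 0.2520, and their cubes sum to 0.0766. Whitehead's formula gives

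N = 12 × (2.576 + 1.282)² / [(ln 1.5)² × (1 − 0.0766)] = 1176,

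against the stated 1180. The plan's figure stands.

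**Assumptions for the bias calculation (none is in the documents).**
- A fraction m of Month 6 survivors (good, moderate, severe) lacks a Month 6 GOS but has a Month 3 GOS.
- A fraction r (0.2 or 0.4) of missing survivors in the top two categories was one category worse at Month 3. Missing severe-disability survivors had not changed.
- The vegetative/dead group is fully known.
- The POM is fitted to expected proportions with 590 per arm. Rejection uses the final critical value 2.58 and ignores the interim look.

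**One case in full: r = 0.4, m = 10% BHR-100, 5% placebo, true OR 1.50.**

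Placebo after carry-forward (share moved 0.05 × 0.4 = 0.02):
- good: 0.31 × 0.98 = 0.3038
- moderate: 0.21 × 0.98 + 0.31 × 0.02 = 0.2120
- severe: 0.19 + 0.21 × 0.02 = 0.1942
- vegetative/dead: 0.2900

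BHR-100 (share moved 0.10 × 0.4 = 0.04):
- good: 0.4026 × 0.96 = 0.3865
- moderate: 0.2165 × 0.96 + 0.4026 × 0.04 = 0.2239
- severe: 0.1669 + 0.2165 × 0.04 = 0.1756
- vegetative/dead: 0.2140

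Odds ratios at the three cuts:
- good versus rest: 0.6300 / 0.4364 = 1.444
- good or moderate versus rest: 1.5667 / 1.0653 = 1.471
- alive and not vegetative versus rest: 3.672 / 2.448 = 1.500

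The fitted common OR is 1.467.

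**Carry-forward results (each range covers r = 0.2 to 0.4).**

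| Missing, BHR-100 vs placebo | True OR 1.50 reads | Power | True OR 1.00 reads |
|---|---|---|---|
| none | 1.500 | 90% | 1.000 |
| 10% vs 10% | 1.493-1.497 | 89% | 1.000 |
| 5% vs 2% | 1.48-1.49 | 87-89% | 0.991-0.995 |
| 10% vs 5% | 1.467-1.483 | 86-88% | 0.984-0.992 |
| 5% vs 10% | 1.51-1.52 | 91-92% | 1.008-1.016 |

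At 10% versus 5% under the null, two-sided rejection is 0.0101-0.0107, against 0.0099 with nothing missing.

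**Equal missingness does not remove the problem if recovery differs.** With 10% missing in both arms, and r = 0.40 in BHR-100 (0.20 for severe disability) against 0.10 in placebo (0.05), OR 1.50 reads 1.449 and a null reads 0.972.

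**The observed-values check.** It keeps known deaths and drops surviving non-returners. At 10% versus 5% missing, the survivor odds ratio at the lowest cut becomes 1.5 × 0.90 / 0.95 = 1.421. The fitted common OR is 1.454 for a true 1.50 and 0.964 for a true null. Both lie further from the truth than carry-forward, on the same side. The ordering is not universal. In the equal-missingness, unequal-recovery case above, the observed-values analysis gives 1.506 and 1.000 and does better than carry-forward.

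**The alternative.** Imputation that predicts Month 6 from Month 3 and arm returns 1.50 and 1.00 in expectation in these scenarios, where data are missing at random.

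**The case against.** The strongest reply is that this hardly matters. The plan expects little missing data. Protocol 4.3 asks for repeated contact attempts and for follow-up at another site after relocation, and site staff are blinded. Every missingness and recovery rate above is assumed. The standard error of the log OR is about 0.105, so the null bias at 10% versus 5% is only ln(0.992) to ln(0.984), or 0.08 to 0.15 standard errors. The trial also runs under a Special Protocol Assessment (SAP 1.1), so a new primary imputation rule may need regulatory agreement late in the study.

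Most of this stands on size and none of it on method. Protocol 10.3 gives one route by which recovery could itself cause loss: a subject who regains competence and declines consent leaves the trial at once. Unequal or informative loss is therefore conceivable, though nothing shows that it is expected.

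A reader might infer two stronger conclusions that the documents do not support:

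- **That the rule works against BHR-100.** The direction depends on which arm loses more survivors or has more recovery among them. Heavier placebo loss inflates the OR.
- **That every non-returning survivor is scored as unchanged.** Carry-forward needs a Month 3 GOS. Subjects with neither score get a covariate-based category, and known deaths are set to Dead.

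**Conclusion.** The point holds as a cheap improvement. The primary analysis uses single-value imputation that assumes no change after Month 3 and carries no imputation uncertainty. The bias can go either way. Under the stated assumptions it is about 0.02 to 0.03 on an OR of 1.50 at 10% versus 5% missing, with 2 to 4 points of power lost or 1 to 2 gained according to direction. It is negligible with equal missingness and equal recovery, and small if missing data are as few as the plan expects. The effect on type I error at these rates is slight. The understatement of the standard error is certain in kind but has not been quantified.

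The safeguard is the weaker part. With differential loss of survivors, the observed-values analysis can err on the same side as carry-forward and by more. Agreement between the two would not show that the imputation had no effect.

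**What to change.** Before unblinding, amend SAP Section 5 and 9.5.1 so that multiple imputation is the primary method:

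- Fix known deaths as Dead first.
- Impute Month 6 GOS from an ordinal model with treatment, the primary covariates (region, age, GCS motor score, pupil response, CT classification) and Month 3 GOS where available. Draw from the predicted probabilities; do not assign the mode.
- Use about 50 imputations and combine the POM results by Rubin's rules.
- Keep carry-forward and observed values as sensitivity analyses.
- Add a tipping-point analysis that varies the imputed outcomes separately by arm, because multiple imputation is itself correct only if data are missing at random.

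The cost is SAP wording, modest programming and a slightly wider interval. All inputs are already collected, so no visits or patients are added. Agreement under the Special Protocol Assessment may be needed. If it cannot be obtained in time, leave the primary rule as it is and pre-specify the multiple imputation and tipping-point analyses as the key sensitivity analyses.
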